#### **6.4.2 Sample Size Considerations**

For our pilot study, we will recruit 30 subjects. While we did not conduct a power calculation for this pilot study, we conducted a similar pilot study with 10 participants in our earlier work with multiple menthol concentrations, and do not anticipate any problems with identifying differences in coolness between the WS-3 and menthol concentrations. For the main study, we will recruit 66 subjects. With an anticipated dropout of 10%, 60 subjects are expected to have complete data. Because we have 4 primary hypotheses (each WS-3 concentration X each menthol concentration > menthol concentration alone), we used a Bonferroni-corrected alpha=0.1. With N=60 completers and a SD of paired differences of 25 as observed in our prior data, we have 80% power to detect a difference of 11.4 (moderate effect size  $d'=.45$ ) in liking/wanting (0-100 scale) between each WS-3 concentration X each menthol concentration and menthol alone using a paired t-test at alpha=0.01.

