# Synopsis

## Primary Objective

The primary objective of this study is to examine the appeal and addiction potential of e-cigs containing WS-3, WS-23 (synthetic coolants), with and without menthol, and nicotine. A pilot study will determine appropriate concentrations of WS-3, WS-23, and menthol.

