## 4 Study Objectives

### 4.1 Hypothesis

We aim to examine the impact of cooling components of WS-3, WS-23, and menthol on the appeal and addiction potential of nicotine-containing e-liquids among adults. We hypothesize that any addition (low, high) of WS-3, WS-23, or menthol will result in similar increases in addiction potential, and that when WS-3, WS-23, and menthol are combined they will produce additive effects relative to menthol alone. We also hypothesize similar changes in appeal outcomes.

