### **6.4 Statistical Method**

#### **6.4.1 Statistical Design**

Preliminary analyses will provide an overview of the data (e.g., randomization success, outcome distribution, missingness patterns). Outcome analyses will be intent-to-treat and use mixed-effects models which allow for different numbers of observations/subject, use all available data, and can handle missing-at-random data. If model assumptions will appear to be violated, we will transform the data or fit more flexible generalized linear or nonparametric mixed models. For the pilot study, separate mixed-effects models will examine the influence of different concentrations of menthol, WS-23 and WS-3 on coolness and overall intensity and will be used to select the concentrations of menthol and WS-3 that product the weak but detectable coolness and the maximum coolness. For the main study, separate mixed-effects model will include menthol (0, Concentration 1, Concentration 2), WS-3 (0, Concentration 1, Concentration 2), WS-23 (0, Concentration 1, Concentration 2, Concentration 3) and time within lab as factors, all interactions among those factors and adjust for stratification variables. A combination of random effects and structured variance-covariance matrices will be used to account for within-subject correlations. The best-fitting structure will be selected based on Akaike information criterion (AIC). For the main study, higher liking/wanting for WS-3 (at Concentration 1 or 2) or WS-23 (at Concentration 1 or 2 or 3) combined with menthol (at Concentration 1 or 2), compared to menthol alone, will be supportive of the primary hypothesis. Similar models will examine the other outcomes and interactions of different concentration combinations of WS-3, WS-23 and menthol with nicotine. Exploratory analyses will also consider the impact of sex, combustible tobacco use and nicotine dependence on experiences from WS-3, menthol and nicotine.

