### **6.5 Planned Analyses**

#### **6.5.1 Primary, Secondary, and Exploratory Objective Analysis**

For the pilot study, separate mixed-effects models will examine the influence of 5 different concentrations of menthol and WS-3 on coolness and overall intensity and will be used to select the concentrations of menthol and WS-3 that product the weak but detectable coolness and the maximum coolness. For the main study, separate mixed-effects model will include menthol (0, Concentration 1, Concentration 2), WS-3 (0, Concentration 1, Concentration 2), WS-23 (0, Concentration 1, Concentration 2, Concentration 3), and time within lab as factors, all interactions among those factors and adjust for stratification

variables. A combination of random effects and structured variance-covariance matrices will be used to account for within-subject correlations. The best-fitting structure will be selected based on Akaike information criterion (AIC). For the main study, higher liking/wanting for WS-3 (at Concentrations 1 or 2) or WS-23 (at Concentrations 1 or 2 or 3) combined with menthol (at Concentration 1 or 2), compared to menthol alone, will be supportive of the primary hypothesis. Similar models will examine the other outcomes and interactions of different concentration combinations of WS-3/WS-23 and menthol with nicotine. Exploratory analyses will also consider the impact of sex, combustible tobacco use and nicotine dependence on experiences from WS-3/WS-23, menthol and nicotine.

Oral microbiome and inflammatory marker assessment will serve as another exploratory objective in this study. Microbial testing, including DNA extraction, library preparation and sequencing methods, will be performed at the CosmosID lab. The analysis will evaluate alpha and beta diversity across different flavor-use groups, with the significance of group-wise clustering determined using a permutational multivariate analysis of variance (MANOVA). Statistical methods such as ANOVA, t-tests and chi-square will assess between-group differences, while controlling for nicotine concentration based on total nicotine equivalents measured in urine samples from participants.

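### Section 6.4.2 prints the Bonferroni-corrected alpha as 0.1 but calculates at 0.01, and its 4 WS-3 contrasts leave out the 6 WS-23 contrasts that 6.4.1 and 6.5.1 also count towards the primary hypothesis

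*Combined protocol and SAP*

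**What the plan says.** Section 6.4.2 defines the primary family and its threshold: "Because we have 4 primary hypotheses (each WS-3 concentration X each menthol concentration > menthol concentration alone), we used a Bonferroni-corrected alpha=0.1". The following sentence gives the inputs, "With N=60 completers and a SD of paired differences of 25 as observed in our prior data", and claims 80% power for a difference of 11.4 points between each WS-3 by menthol combination "and menthol alone using a paired t-test at alpha=0.01".

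Section 6.4.1 says what will count as support: "higher liking/wanting for WS-3 (at Concentration 1 or 2) or WS-23 (at Concentration 1 or 2 or 3) combined with menthol". The sentence continues: "combined with menthol (at Concentration 1 or 2), compared to menthol alone, will be supportive of the primary hypothesis". Section 6.5.1 repeats the rule: "higher liking/wanting for WS-3 (at Concentrations 1 or 2) or WS-23 (at Concentrations 1 or 2 or 3) combined with menthol".

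WS-23 is also part of the stated purpose. The Synopsis gives the primary objective as to "examine the appeal and addiction potential of e-cigs containing WS-3, WS-23 (synthetic coolants), with and without menthol, and nicotine". Section 4.1 hypothesises that "when WS-3, WS-23, and menthol are combined they will produce additive effects relative to menthol alone". Section 4.2 includes three WS-23 concentrations in the primary objective.

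No section states the familywise error rate, whether the tests are one- or two-sided, or whether a single significant contrast is enough.

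**The concern.** There are two separate problems.

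First, adjacent sentences give thresholds of 0.1 and 0.01 for the same four contrasts. Section 6.4.2 is the only place where the plan states an alpha for the primary comparisons. An analyst who took the printed corrected value literally would use a threshold ten times larger than the one behind the sample size.

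Second, the count of four covers WS-3 only. The analysis sections join WS-3 and WS-23 with an or, so a positive WS-23 contrast can be presented as support for the primary hypothesis although it was never counted in the correction or powered. With the familywise rate and sidedness unstated, the choice of what counts as a controlled result could be made after the results are seen.

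**Working it through.** **Inputs.** From 6.4.2: N = 60 completers, SD of paired differences 25, difference 11.4, 80% power, paired t-test. From 6.4.1 and 6.5.1: 2 WS-3 levels, 3 WS-23 levels and 2 non-zero menthol levels, each compared with menthol alone.

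**Step 1: reproduce the plan's figure.** Power comes from the noncentral t distribution with 59 degrees of freedom and noncentrality 11.4/25 × √60 = 0.456 × 7.746 = 3.53. For a two-sided 0.01 test the critical value is 2.662, which gives 80.4% power. The difference detectable with 80% power is 11.35 points. The plan's statement is therefore reproduced.

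**Step 2: try the other thresholds on the same inputs.**

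| Per-test alpha | Power for 11.4 points | Difference detectable at 80% power |
|---|---|---|
| 0.1 two-sided | 96.8% | 8.12 |
| 0.0125 two-sided (0.05/4) | 82.7% | 11.07 |
| 0.01 two-sided | 80.4% | 11.35 |
| 0.01 one-sided | 87.0% | 10.47 |
| 0.05/6 = 0.0083 two-sided | 78.5% | 11.57 |
| 0.005 two-sided (0.05/10) | 72.8% | 12.18 |
| 0.005 one-sided | 80.4% | 11.35 |
| 0.0025 one-sided (0.025/10) | 72.8% | 12.18 |

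The calculation was not done at 0.1, and 0.1 is not a Bonferroni value for four tests at an overall 5% (0.05/4 = 0.0125). The 0.01 may be 0.0125 rounded down; it is slightly stricter. A two-sided 0.01 test and a one-sided 0.005 test share a critical value, so the stated power fits either.

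**Step 3: count the contrasts.** WS-3: 2 × 2 = 4. WS-23: 3 × 2 = 6. Total 10, of which 6.4.2 covers 4.

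**Step 4: familywise error if any one contrast suffices.** The Bonferroni bound is the number of contrasts times alpha. The simulation used 100,000 null replicates with n = 60. At each of the two menthol levels, 2 or 5 contrasts share one menthol-alone control. Menthol levels are taken as independent and variances as equal.

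| Family and per-test alpha (two-sided) | Either direction: simulated (bound) | Higher only: simulated (bound) |
|---|---|---|
| 4 contrasts, 0.01 | 3.8% (4%) | 1.9% (2%) |
| 10 contrasts, 0.01 | 8.3% (10%) | 4.2% (5%) |
| 10 contrasts, 0.0125 | about 10% (12.5%) | about 5.2% (6.25%) |
| 10 contrasts, 0.005 | about 4.4% (5%) | about 2.2% (2.5%) |

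At the 0.01 actually used, the four WS-3 contrasts are controlled. Over all ten, a 5% rate holds for claims of higher liking/wanting, but not for claims in either direction.

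**The case against.** The strongest reply is that little harm follows. The 0.1 is contradicted by the next sentence, and only 0.01 yields the stated power, so on its own it is an editorial slip. The analysis sections count only higher liking/wanting as support, and 6.4.2 writes its hypotheses with a greater-than sign. For claims in that direction a two-sided 0.01 test spends 0.005 per contrast, and 10 × 0.005 = 5%. The existing threshold thus already covers the WS-23 contrasts, and the two-sided 5% standard that it fails is one the plan never sets. This stands, and it is why the point is not rated higher. It does not close the matter, because whether 5% is met depends on a sidedness and a familywise rate that are written nowhere.

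It can also be said that ten is not the only possible count. Section 4.1 refers to low and high levels only, the primary objective includes conditions without menthol, section 5.2.1 lists several sensory ratings as primary outcomes alongside liking/wanting, and the secondary objective already covers interactions among WS-3, WS-23 and menthol. Those observations are fair, but they do not remove the conflict over liking/wanting: 6.4.2 counts four contrasts, while 6.4.1 and 6.5.1 describe ten.

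Finally, the planned analysis is a mixed model, so the paired-t figures are approximate. They do use the same method as the plan's own calculation.

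**Conclusion.** Both parts hold. The printed 0.1 is a misprint for 0.01; it does not affect the sample size, and the power stated for the WS-3 contrasts is right at two-sided 0.01. Six of the ten contrasts that can support the primary hypothesis have no error-rate or power statement.

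The practical inflation is modest: about 8.3% in either direction and about 4.2% for higher liking/wanting, assuming that one significant contrast suffices, that the menthol levels are independent and that variances are equal. Any detectable difference quoted for WS-23 assumes that the SD of 25, which the plan gives in its WS-3 calculation, also applies to WS-23. This should be fixed before the data are analysed, but it does not undermine the design.

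**What to change.** Correct the 0.1 in 6.4.2. Then state the same five items in 6.4.1, 6.4.2 and 6.5.1: the family, the familywise alpha, the sidedness, the per-test alpha, and whether one significant contrast is enough. Two routes are available.

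**(a) All ten contrasts primary.** At a two-sided 5% familywise rate use 0.05/10 = 0.005 per test, or Holm, and restate the difference detectable at 80% power as 12.2 points (d about 0.49), noting the assumed SD for WS-23. If a one-sided 5% rate is chosen, 0.005 one-sided keeps 11.4 points; at one-sided 2.5% (0.0025 per test) the figure is again 12.2.

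**(b) The four WS-3 contrasts primary at two-sided 0.01.** Name the six WS-23 contrasts as a secondary family, for example at 0.05/6 = 0.0083 two-sided, which detects 11.6 points if the SD is 25. The primary objective in the Synopsis and sections 4.1 and 4.2 would need editing, the sentence on support for the primary hypothesis in 6.4.1 and 6.5.1 would be limited to WS-3, and the new family should be squared with the existing secondary objective on interactions.

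**Cost.** Neither route adds participants. Two-sided (a) lowers power for 11.4 points from 80.4% to 72.8%; restoring 80% would take 68 completers (68/0.9, so 76 recruited), which is optional. One-sided (a) gives up any formal claim that a coolant lowers liking/wanting. Route (b) makes WS-23 secondary. Either change goes to the IRB as an amendment, as section 7.2 requires for any protocol change.

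### The only multiplicity rule is a single-step Bonferroni level in the sample-size section; naming Holm's step-down test in the analysis section would confirm more of the four primary contrasts at the same family-wise error

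*Combined protocol and SAP*

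**What the plan says.** Section 6.4.2 (Sample Size Considerations) defines the family: "Because we have 4 primary hypotheses (each WS-3 concentration X each menthol concentration > menthol concentration alone"). It then says "we used a Bonferroni-corrected alpha", printed as 0.1, and bases the power on a comparison with "menthol alone using a paired t-test at alpha=0.01". The inputs are given as "With N=60 completers and a SD of paired differences of 25 as observed in our prior data", and the result as "we have 80% power to detect a difference of 11.4" points in liking/wanting on a 0-100 scale.

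No other place in the documents mentions a multiplicity correction. Sections 6.4.1 and 6.5.1 specify mixed-effects models and no adjustment. They count a higher score for either WS-3 concentration, or any of the three WS-23 concentrations, combined with either menthol concentration, as support for the primary hypothesis.

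Section 4.1 predicts that "any addition (low, high) of WS-3, WS-23, or menthol will result in similar increases in addiction potential", with additive effects when the coolants are combined with menthol.

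**The concern.** Single-step Bonferroni holds every contrast to the strictest threshold, however many of the others have already been rejected. Holm's procedure relaxes the threshold after each rejection. It controls the family-wise error under any dependence, and at the same level it rejects everything that Bonferroni rejects.

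The difference matters most when several effects are real at once, which is what section 4.1 predicts. Section 6.4.2 also treats each concentration pair as a primary hypothesis of its own, so which pairs are confirmed is part of the result. The stated 80% is for one contrast at a time; the plan gives no power for confirming several. If the Bonferroni level is carried into the analysis by default, because no other rule is written down, true effects of the planned size will be missed more often than they need be.

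**Working it through.** **Inputs from section 6.4.2.** Four contrasts; n = 60; SD of paired differences 25; difference 11.4; per-test alpha 0.01. Sidedness is not stated.

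**Step 1: reproduce the plan's figure.** Standardised difference 11.4/25 = 0.456. Noncentrality 0.456 × √60 = 3.53, with 59 degrees of freedom. Noncentral-t power of a paired t-test:

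| Alpha per test | Power at 11.4 | Difference for 80% power |
|---|---|---|
| 0.01 two-sided | 80.4% | 11.35 |
| 0.01 one-sided | 87.0% | 10.47 |
| 0.0125 two-sided | 82.7% | 11.07 |
| 0.1 two-sided | 96.8% | 8.12 |

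The stated 80% and 11.4 reproduce at two-sided 0.01. The printed 0.1 does not fit. Four tests at 0.01 give a family-wise bound of 4 × 0.01 = 0.04; exact Bonferroni for 0.05 is 0.05/4 = 0.0125.

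**Step 2: the two rules.** Order the p-values from smallest to largest. Bonferroni compares all four with α/4. Holm compares them in turn with α/4, α/3, α/2 and α, stopping at the first failure. At α = 0.05 the Holm thresholds are 0.0125, 0.0167, 0.025 and 0.05. The first step is the same in both rules, so the chance of at least one rejection is identical.

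**Step 3: correlation between contrasts (assumed; the documents give none).** The two WS-3 contrasts at one menthol level share the menthol-alone condition. If the errors are independent with variance s², each difference has variance 2s² and the two have covariance s², so their correlation is s²/2s² = 0.5. Contrasts at different menthol levels use different comparators, which gives 0. Independence and 0.5 throughout were run as a range.

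**Step 4: simulation of four correlated two-sided paired t-tests, true difference 11.4 in all four.** Chance of rejecting all four:

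| Correlation within / across menthol levels | Family-wise level | Bonferroni | Holm | Gain (points) |
|---|---|---|---|---|
| 0.5 / 0 | 0.05 | 52.3% | 77.4% | 25.1 |
| 0.5 / 0 | 0.04 | 47.7% | 73.4% | 25.7 |
| 0 / 0 | 0.05 | 46.4% | 75.2% | 28.8 |
| 0 / 0 | 0.04 | 41.5% | 70.5% | 29.0 |
| 0.5 / 0.5 | 0.05 | 59.8% | 80.3% | 20.5 |
| 0.5 / 0.5 | 0.04 | 55.9% | 77.0% | 21.1 |

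At 0.5 / 0 and family-wise 0.05, average power per contrast goes from 82.7% to 91.2%. The chance of at least one rejection is 99.5% under both rules.

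**Step 5: fewer or smaller real effects (0.5 / 0, family-wise 0.05).**

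- Two of four real: average power for the real contrasts rises by about 2 points, from 82.6% to 84.5%.
- One of four real: it moves by about 0.1 point, from 82.2% to 82.3%.
- All four real but one at half size (5.7): all four are rejected 15% of the time with Bonferroni and 35% with Holm.

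**Step 6: if WS-23 is also primary.** Two WS-3 and three WS-23 concentrations at two menthol levels give (2 + 3) × 2 = 10 contrasts, and Bonferroni for 0.05 becomes 0.005 per test. Per-contrast power at 11.4 is then 72.8%. With all ten effects real and the same correlation pattern, average power goes from about 73% to 86%, and the chance of confirming all ten from about 16% to 57%.

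**The case against.** The strongest reply is that the plan is valid as it stands. Bonferroni appears only in the sample-size section, and sizing at that level is compatible with a Holm analysis later. A reader might infer that the plan commits to fixed-level Bonferroni testing, but the analysis sections do not say so. What stands is that no other rule is written anywhere.

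A reader might also infer that the trial succeeds only if all four contrasts are significant, so that it would fail about half the time. Nothing in the documents sets that rule. The criterion in 6.4.1 and 6.5.1 is worded with 'or', and on that criterion Holm gains nothing. The gain concerns how many of the separately counted hypotheses are confirmed, and average power per contrast shows it without any all-four rule.

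It is tempting to compare the plan's 0.01 per test with Holm at 0.05, which gives about 48% against 77% for all four. That sets a family-wise level of 0.04 against 0.05, and about 4 points of the difference come from the larger alpha. Only the equal-level pairs are a fair measure.

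Nor does the shared menthol-alone comparator enlarge the all-four gain. Positive correlation shrinks it, from about 29 points with independent contrasts to about 20 with correlation 0.5 throughout.

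Finally, single-step Bonferroni has simple matching confidence intervals and Holm does not. That is a real but small cost.

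**Conclusion.** The point holds as an inexpensive improvement to a valid plan. The documents contain one multiplicity rule, a single-step Bonferroni level used for sizing, and the analysis sections contain none. Holm at the same family-wise level is never worse. If all four effects are real at 11.4 points, with n = 60, SD 25 and correlation 0.5 within and 0 across menthol levels, it adds about 8 to 9 points of average power per contrast and about 25 points to the chance of confirming all four.

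The absolute percentages depend on the assumed correlation and on four equal effects of the planned size. The direction does not. The benefit shrinks quickly as fewer effects are real, and it is nil for the chance of at least one rejection.

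**What to change.** In 6.5.1, list the primary liking/wanting contrasts: the four WS-3 contrasts, or all ten if the WS-23 contrasts are also primary. State that they are tested by Holm's step-down procedure at two-sided family-wise alpha 0.05, using the contrast p-values from the mixed model.

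In 6.4.2, reconcile the printed alpha of 0.1 with the 0.01 used in the calculation, and state the sidedness. Keep the 80% power at 0.01 as a conservative lower bound if the family is four; restate it if the family is ten.

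Report Bonferroni-level confidence intervals alongside the Holm decisions, because intervals that match Holm are less simple. The cost is a sentence or two of text, with no added participants, visits or measurements.

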### **6.5 Planned Analyses**

#### **6.5.1 Primary, Secondary, and Exploratory Objective Analysis**

For the pilot study, separate mixed-effects models will examine the influence of 5 different concentrations of menthol and WS-3 on coolness and overall intensity and will be used to select the concentrations of menthol and WS-3 that product the weak but detectable coolness and the maximum coolness. For the main study, separate mixed-effects model will include menthol (0, Concentration 1, Concentration 2), WS-3 (0, Concentration 1, Concentration 2), WS-23 (0, Concentration 1, Concentration 2, Concentration 3), and time within lab as factors, all interactions among those factors and adjust for stratification

variables. A combination of random effects and structured variance-covariance matrices will be used to account for within-subject correlations. The best-fitting structure will be selected based on Akaike information criterion (AIC). For the main study, higher liking/wanting for WS-3 (at Concentrations 1 or 2) or WS-23 (at Concentrations 1 or 2 or 3) combined with menthol (at Concentration 1 or 2), compared to menthol alone, will be supportive of the primary hypothesis. Similar models will examine the other outcomes and interactions of different concentration combinations of WS-3/WS-23 and menthol with nicotine. Exploratory analyses will also consider the impact of sex, combustible tobacco use and nicotine dependence on experiences from WS-3/WS-23, menthol and nicotine.

Oral microbiome and inflammatory marker assessment will serve as another exploratory objective in this study. Microbial testing, including DNA extraction, library preparation and sequencing methods, will be performed at the CosmosID lab. The analysis will evaluate alpha and beta diversity across different flavor-use groups, with the significance of group-wise clustering determined using a permutational multivariate analysis of variance (MANOVA). Statistical methods such as ANOVA, t-tests and chi-square will assess between-group differences, while controlling for nicotine concentration based on total nicotine equivalents measured in urine samples from participants.

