## Number of Participants

30 participants for the pilot study, 66 participants for the main study. Up to 33 exclusive e-cigarette users enrolled in the main study will be recruited for oral microbiome and inflammatory marker assessments.

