**Secondary and Exploratory Outcome Variables (if applicable)**

E-Cigarette Craving: The Yale Craving Scale

Salivary Nicotine/Cotinine Levels

Oral microbiome, inflammatory markers, and self-reported oral health status in exclusive e-cigarette users, compared by past-month e-cigarette flavor use.

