### 4.4 Exploratory Objectives (if applicable)

An exploratory objective of this study is to examine the influence of predictors such as sex, combustible tobacco use, and nicotine dependence on study outcomes.

Another exploratory objective is to examine oral microbiome, salivary inflammatory markers and self-reported oral health status in exclusive e-cigarette users and compare the differences among users of different e-cigarette flavor groups (1. Mint/menthol, 2. fruit/sweet, 3. tobacco). We hypothesize that users of mint/menthol or fruit/sweet flavors will have higher levels of anaerobic bacteria in their oral microbiome, greater inflammatory markers in saliva, and poorer oral health compared to tobacco flavor users.

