**Main Study:** The purpose of the main study will be to determine sensory responses following exposure to e-liquids containing nicotine and WS-3, WS-23, and menthol. This study will recruit 66 adult e-cigarette users (50% with current cigarette use, of which 50% will use menthol cigarettes), to participate in 3 laboratory sessions, separated by at least 24 hrs. At the intake visit, participation in the oral microbiome and inflammatory marker testing will be optional for exclusive e-cigarette users (up to 33). Specifically, they will be asked to provide saliva and urine samples for oral microbiome and inflammatory marker testing and complete a brief survey about their oral health status. Additionally, participants will be asked to submit their most used e-cigarette device/pods from the past-month for analysis. These will be used as exploratory assessments. During the lab visits, participants will receive all eighteen conditions shown in Table 2 below and will be asked to abstain from tobacco use for two hours prior to session start (to control for time since last tobacco exposure). Participants will be randomized to receive one of the 3 menthol conditions (no-menthol, low menthol, high menthol, levels determined by the pilot study above) in Lab 1 and will receive the alternative conditions in randomized order in Lab 2 and Lab 3. During each lab session the menthol condition will be paired with three WS-3 concentrations: no WS-3, low (0.1%) WS-3, or high (2.0%) WS-3 and three WS-23 concentrations: low (0.1%) WS-23, high (2.0%) WS-23, or 4% WS-23 (concentration determined by pilot study) in randomized order. All e-cigarettes will contain nicotine salt at a nicotine concentration of ~59mg/ml, commensurate with levels in popular commercially available nicotine salt e-cigarettes. Each exposure will consist of a 5-puff bout (each puff 3-sec long and separated by 30 sec.) collected via a puff topography device (an apparatus used to measure puffing behavior) and will be separated by 30 mins to allow any sensory effects to dissipate between exposures. To precisely measure puffing behavior, we will utilize a validated electronic cigarette topography device (eTop). This device connects to a computer with software designed to measure puffing behavior. An e-cigarette is inserted into a silicone mouthpiece and the mouthpiece is connected to tubing which feeds into the device. As a participant inhales this device measure puffing behavior including number of puffs, puff volume, puff duration, puff flow rate (a calculation of volume/time). These indices help us understand vaping behavior and make it possible to compare e-cigarette exposure across participants. Topography mouthpieces are sanitized in between subjects and inhaling e-cigarettes via topography devices present no increased risk to participants. At the end of each of the three lab sessions, participants will choose between the 6 e-liquids they sampled in the lab using a free-choice paradigm (~30 mins).

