### **5.3.1 Number of Participants**

We aim to recruit 30 adults for the pilot study and 66 adults for the main study (33 with current cigarette use, 16 reporting menthol cigarette use). In the main study, we will recruit a subset of eligible exclusive e-cigarette users (up to 33) for oral microbiome and inflammation assessment.

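### The permutational MANOVA planned for microbiome clustering cannot separate a difference in spread between flavour groups from a difference in composition, and no dispersion check is planned (exploratory objective, minor)

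*Combined protocol and SAP*

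**What the plan says.** Section 4.4 sets an exploratory objective to "compare the differences among users of different e-cigarette flavor groups (1. Mint/menthol, 2. fruit/sweet, 3. tobacco". Its hypothesis concerns levels: more anaerobic bacteria, more inflammation and poorer oral health in mint/menthol or fruit/sweet users than in tobacco-flavour users.

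Section 6.5.1 states the analysis: "The analysis will evaluate alpha and beta diversity across different flavor-use groups". The test that decides whether the groups cluster follows in the same sentence: "with the significance of group-wise clustering determined using a permutational multivariate analysis of variance (MANOVA". It then lists ANOVA, t-tests and chi-square for between-group differences, controlling for urinary nicotine equivalents. It names no distance measure, number of permutations, dispersion test or rule for reading a significant result.

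The groups are observed, not assigned: the synopsis has the outcomes assessed "in exclusive e-cigarette users, compared by past-month e-cigarette flavor use". Section 5.3.1 says "we will recruit a subset of eligible exclusive e-cigarette users (up to 33) for oral microbiome", and section 5.1 adds that "participation in the oral microbiome and inflammatory marker testing will be optional for exclusive e-cigarette users (up to 33". No flavour quota or group size appears anywhere. Section 6.5.1 confirms the status: "Oral microbiome and inflammatory marker assessment will serve as another exploratory objective in this study".

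**The concern.** Clustering by flavour means that the groups differ in average community composition, which is also what the section 4.4 hypothesis is about. A label-shuffling test has a broader null: the groups are exchangeable, so they share both centroid and within-group spread. The usual pseudo-F pools within-group variation in proportion to group size. When sizes and spreads both differ, it is too large if the smallest group is the most variable and too small if the smallest group is the least variable.

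Nothing in the plan ensures equal groups. Flavour is self-selected, participation is optional, and section 5.3.2 adds exclusions for this subset. Section 2.2 describes cooling and fruity-cooling products as popular, so a small tobacco group is plausible, although the documents do not say so.

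Nothing planned would reveal the problem either. The remedies for violated model assumptions in sections 6.4.1 and 6.5.8 are transformations or other mixed models for the outcome analyses, and they do not bear on a permutation test. A significant result could be published as flavour-related clustering when only variability differs, and a non-significant one could conceal a real shift.

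**Working it through.** **Plan's own figure.** There is none for this analysis, so there is nothing to reproduce.

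**Inputs from the documents.** Three groups (4.4); at most 33 people (5.3.1); permutational MANOVA (6.5.1).

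**Assumed inputs.** Group sizes, spread ratios, distance measure, number of taxa, and a 5% level.

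**Step 1: direction, by expected mean squares.** Take Euclidean distance, equal centroids, group sizes n_j, SDs s_j, N = 33 and k = 3. Per variable:

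- E(within) = Σ(n_j − 1)s_j² / (N − k)
- E(between) = Σ(1 − n_j/N)s_j² / (k − 1)

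With equal spread the ratio between/within is 1. With unequal spread:

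- 14/14/5, SD 1/1/1.5: within = (13 + 13 + 4×2.25)/30 = 1.167; between = (19/33 + 19/33 + 28/33×2.25)/2 = 1.530; ratio 1.31.
- 14/14/5, SD 1.5/1.5/1: within = (13×2.25 + 13×2.25 + 4)/30 = 2.083; between = (19/33×2.25 + 19/33×2.25 + 28/33)/2 = 1.720; ratio 0.83.
- 11/11/11: both expressions reduce to Σs_j²/3, so the ratio is 1 whatever the spreads.

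The bias therefore goes up or down according to which group is more variable, and with this distance it vanishes in expectation when sizes are equal.

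**Step 2: size, by simulation.** Log-ratio abundances of 60 taxa (6 latent factors plus noise), identical group means, Euclidean (Aitchison) distance, 1500 data sets per cell, 399 permutations. Rejection at nominal 5%:

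| Sizes | SDs | Pseudo-F | Welch-type Wd* |
|---|---|---|---|
| 14/14/5 | 1/1/1.25 | 14.3% | 5.5% |
| 14/14/5 | 1/1/1.5 | 24.0% | 5.3% |
| 14/14/5 | 1/1/2 | 49.6% | 5.3% |
| 14/14/5 | 1.5/1.5/1 | 1.2% | 5.8% |
| 14/13/6 | 1/1/1.25 | 11.4% | 5.1% |
| 14/13/6 | 1/1/1.5 | 20.8% | 4.9% |
| 14/13/6 | 1/1/2 | 39.2% | 4.9% |
| 14/13/6 | 1.5/1.5/1 | 1.7% | 4.7% |
| 11/11/11 | various | 4.9-6.9% | 4.9-5.6% |

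Repeat runs with log-ratio distance and these two unequal layouts gave 9-14%, 16-30% and 39-48% for the pseudo-F at ratios 1.25, 1.5 and 2, about 1% with the larger groups more variable, and about 4-7% for Wd*.

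**Step 3: sensitivity to the assumptions.** For 14/13/6 and independent normal variables, the pseudo-F over ratios 1.25-2 rejects in 8-19% with 2 variables, 9-26% with 5, 14-53% with 20 and 32-92% with 100. For 14/13/6 with Bray-Curtis distance on 20-taxon compositions it rejects in 12%, 25% and 59%. Bray-Curtis also affects balanced groups: at 11/11/11 one run gave 35% at the largest spread setting, and others reached 45-64% for both statistics. In unequal layouts under Bray-Curtis, Wd* rejected in 5-23%.

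**Step 4: power.** At 14/13/6 with 20 variables and a 2.5 SD shift of the smallest group in one variable:

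| SDs | Pseudo-F | Wd* |
|---|---|---|
| 1/1/1 | 82% | 79% |
| 1.5/1.5/1 | 22% | 70% |
| 1/1/1.5 | 84% | 42% |

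The 84% comes from a test that, without any shift, rejects in 24-28% of data sets at those SDs, so it is not power at the 5% level.

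**The case against.** The strongest reply is that the problem is conditional and of small consequence. It needs unequal spread and, with Euclidean distance, unequal group sizes; the documents state neither. The analysis is exploratory, in an optional subset of at most 33, with no alpha, power claim or decision attached. A difference in spread is itself a real difference between groups, so the fault is one of labelling. All of this stands and limits the severity.

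Several stronger readings are tempting but not supported:

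- A reader might infer that this trial's test has a false-positive rate of 14-50%. That range is one assumed layout (14/14/5) with the smallest group the most variable. In the opposite direction the test is conservative, and other assumptions move the figure widely.
- A reader might infer that balanced groups would remove the problem, or that a Welch-type statistic always holds its level. Both hold in the Euclidean runs and fail in the Bray-Curtis ones. Part of that Bray-Curtis excess may be a true location difference in the distance space, because equal mean composition need not give equal centroids there. Either way, neither assurance can be given until the distance is fixed.
- A reader might infer that Wd* should simply replace the planned test. As a plain group comparison it has no evident place for the continuous nicotine-equivalents covariate, and section 6.5.1 does not make clear whether that adjustment extends to beta diversity. Its power is also lower when the smallest group is the more variable one.

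**Conclusion.** The point holds as a minor one. The only beta-diversity test in section 6.5.1 does not distinguish location from spread, nothing secures balanced flavour groups, and no check is planned that would show which kind of difference was found. For a nominal 5% test with the assumed layouts 14/14/5 or 14/13/6 and Euclidean log-ratio distance, false positives are about 10-50% when the smallest group is 1.25-2 times as variable, and about 1-2% when the larger groups are 1.5 times as variable. These are illustrations. Across the other dimensions, layouts and metrics tried with the small group more variable, the figure runs from about 8% to above 90%. The actual rate in this trial cannot be derived from the documents. The primary and secondary objectives are untouched.

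**What to change.** In section 6.5.1:

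1. Name the distance measure in advance. Aitchison distance is one option, under which the Welch-type statistic held about 4-7% in these checks.
2. Report the number of participants in each flavour group.
3. Report a permutation test of multivariate dispersion beside the permutational MANOVA.
4. Add the Welch-type distance statistic (Wd*), on the same distances and permutations, as the unadjusted test of location. Call a result clustering only if it holds there; otherwise describe it as a possible difference in variability.
5. Keep any permutational MANOVA adjusted for nicotine equivalents as planned, and read it together with the dispersion test.

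The cost is a few sentences and a small extra analysis on the same distance matrix, with no new data, participants or procedures. With equal spread almost no power is lost (49% against 47% and 61% against 60% in the log-ratio runs, pseudo-F first). The downside is fewer nominally significant results when the smallest group is the more variable one.
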